A Multi-Site, Parallel-Group, Randomized Clinical Trial Comparing a Brief Tele-Cognitive Behavioral Therapy Intervention (BRIGHT) with Attention Control for the Reduction of Body Image-Related Distress Among Head and Neck Cancer Survivors

Protocol Number: 103733

National Clinical Trial (NCT) Identified Number: NCT 05442957

Principal Investigator: [name]., M.P.H., FACS

Sponsor: National Cancer Institute

Grant Title: A Randomized Controlled Trial to Evaluate a Novel Treatment Strategy for Body Image-Related Distress Among Head and Neck Cancer Survivors

Grant Number: R37 CA269385

Funded by: NCI

Version Number: v.3.0 (8 February, 2023)

CONFIDENTIALITY STATEMENT

This document is confidential communication. Acceptance of this document constitutes agreement by the recipient that no unpublished information contained herein will be published or disclosed without prior approval of the Principal Investigator or other participating study leadership and as consistent with the NIH terms of award.

PROTOCOL VERSION HISTORY

1.2 Schema: Updated to reflect changes to stratification variables for randomization (see **6.3** below) and more clearly illustrate study endpoints.

1.3 Schedule of Activities: Corrected erroneous omission of intervention session 6 from Schedule of Activities in Protocol v2.0 (8 December 2022). Addressed downstream ramifications to other aspects of the Schedule of Activities created by adding a column for intervention session 6.

5.4 Screen Failures: Clarified definition of screen failure and circumstances for re-screening.

6.2 Fidelity: Changed from 20% of sessions to 17% of sessions to harmonize with prior change from 5 to 6 intervention sessions.

6.3 Measures to Minimize Bias: Randomization and Blinding: Added free flap reconstruction (yes/no) as stratification variable for randomization. Protocol harmonized in sections **1.2 (Schema)**, **4.1 (Overall Design)** and **9.4.2 (Analysis of Primary Endpoint)**. Clarified blinding of investigators, patients, and outcome assessors.

8.2 Baseline Assessments: Added baseline patient self-report assessment of history of medication or counseling for mental health disorders (Y/N).

8.3 Endpoint and other Non-Safety Assessments: Added information about scoring all PROMIS measures using the T-distribution. Provided additional details about fidelity assessments.

1 PROTOCOL SUMMARY

1.1 SYNOPSIS

- Title:** A Multi-Site, Parallel-Group, Randomized Clinical Trial Comparing a Brief Tele-Cognitive Behavioral Therapy Intervention (BRIGHT) with Attention Control for the Reduction of Body Image-Related Distress Among Head and Neck Cancer Survivors
- Grant Number:** R37 CA269385
- Study Description:** In this multi-site, parallel-group, randomized clinical trial, we will evaluate the efficacy of BRIGHT compared with attention control (AC) for managing body image distress (BID) among head and neck cancer survivors (HNC) survivors, examine BRIGHT's underlying mechanisms, and characterize factors affecting the future adoption of BRIGHT into clinical care.
- Objectives:**
- Primary Objective:
To evaluate the efficacy of BRIGHT compared with AC on HNC-related BID as measured by change from baseline in the IMAGE-HN score.
- Secondary Objectives:
1. To evaluate the clinical response rate of BRIGHT compared with AC on HNC-related BID as measured by proportion of patients with a clinically meaningful change from baseline in the IMAGE-HN score.
 2. To further evaluate the longer-term efficacy of BRIGHT compared with AC on HNC-related BID as measured by change from baseline in the IMAGE-HN score at 9-month follow-up (post-randomization).
 3. To evaluate the efficacy of BRIGHT compared with AC on psychological and social well-being as measured by change from baseline in Shame and Stigma Scale in HNC, PROMIS SF v1.0-Depression 8a, PROMIS SF v1.0-Anxiety 8a, Beck Scale for Suicidal Ideation, and PROMIS SF v2.0-Ability to Participate in Social Activities-8a scores at 3-, 6-, and 9-month follow-up.
 4. To evaluate the efficacy of BRIGHT compared with AC on quality of life (QOL) as measured by change from baseline in the EORTC QLQ-HN35 score at 3-, 6-, and 9-month follow-up.
 5. To examine the mechanism of change underlying BRIGHT for HNC-related BID as measured by change from baseline in Body Image Coping Strategies Inventory subscale scores and the Automatic Thoughts Questionnaire score.

Endpoints:

Primary Endpoint:

Change in the IMAGE-HN score from baseline to 6-month follow-up

Select Secondary Endpoints:

1. Change in the IMAGE-HN score from baseline to 2-, 3- and 9-month follow-up
2. Proportion of patients with a decrease in the IMAGE-HN score of ≥ 9 points from baseline at 3-, 6-, and 9-month follow-up
3. Change in the Shame and Stigma Scale in HNC score from baseline to 3-, 6-, and 9-month follow-up
4. Change in the PROMIS SF v1.0-Depression 8a score from baseline to 3-, 6-, and 9-month follow-up
5. Change in the PROMIS SF v1.0-Anxiety 8a score from baseline to 3-, 6-, and 9-month follow-up
6. Change in the Body Image Coping Strategies Inventory Avoidance, Positive Rational Acceptance, and Appearance Fixing subscale scores from baseline to 2, 3-, and 6-month follow-up

Study Population:

The study population will consist of adult HNC survivors with HNC-related BID

Phase or Stage:

N/A
The study will be conducted, and participants enrolled, at three sites: (1) the Medical University of South Carolina (MUSC), (2) Henry Ford Health, and (3) Washington University in St. Louis

Description of Study

BRIGHT is 6 sessions of weekly, 60-minute, manualized individual tele-cognitive behavioral therapy based on a transactional coping model of HNC-related BID

Intervention/Experimental

Manipulation:

Study Duration:

49 months

Participant Duration:

9 months

1.2 SCHEMA

[figure not shown]

Fig 1. Schema. In this multisite RCT, HNC survivors with clinically significant HNC-related BID (N=180) from the Medical University of South Carolina (MUSC), Washington University School of Medicine (WUSM), and Henry Ford Health (HFH) will be randomized 1:1 to BRIGHT or AC with randomization stratified by site (MUSC, WUSM, HFH). Patients will complete measures of HNC-related BID (primary endpoint), psychological and social well-being, and mechanisms of change underlying CBT at 2, 3, 6, and 9-month follow-up (post-randomization) to assess the effect of BRIGHT on BID, psychological and social well-being and quality of life, and mechanism of change underlying BRIGHT.

1.3 SCHEDULE OF ACTIVITIES

Table 1. Schedule of Activities for BRIGHT and AC: Screening, Treatment, and Follow-up

Visit Label	Allocation	Screening	Treatment						Follow-up ^b				For Details
			Session						2 m	3 m	6 m	9 m	
			1	2	3	4	5	6	7	8	9	10	
Visit #		1 ^a	--	2	3	4	5	6	7	8	9	10	11
Study Activity													
Enrollment	Eligibility Screen ^c		X										5
	Informed Consent ^d		X										9.5.2
Allocation			X										
Study Intervention	BRIGHT			X	X	X	X	X	X				6.1.1
	AC			X	X	X	X	X	X				6.1.2
Study Assessments													
Baseline	Demographics		X										8.2
	Clinical and Oncologic		X										
Safety	Adverse Events			X	X	X	X	X	X	X	X	X	8.4
Concomitant Meds	Medication Assessment		X		X	X	X	X	X	X	X	X	6.5
Efficacy^e	IMAGE-HN		X							X	X	X	X
	Shame and Stigma Scale		X							X	X	X	X
	PROMIS SF v1.0-Depression 8a		X							X	X	X	X
	PROMIS SF v1.0-Anxiety 8a		X							X	X	X	X
	Beck Scale for Suicidal Ideation ^f		X							X	X	X	X
	PROMIS SF v2.0-Social Activities-8a		X							X	X	X	X
	EORTC QLQ-HN35		X							X	X	X	X
Mechanism	BICSI		X							X	X	X	
	Automatic Thoughts Questionnaire		X							X	X	X	8.3.2
Intervention Fidelity	BRIGHT Fidelity and Competence Scale									X			8.3.3
	Interventionist self-report			X	X	X	X	X	X				
Patient Adherence	Attendance, Homework			X	X	X	X	X	X				8.3.4
Common Factors	WAI-SR-Therapist									X			8.3.3
	Therapist Empathy Scale									X			
	Credibility/Expectancy Questionnaire		X							X			

Table 1. Schedule of Activities for BRIGHT and AC: Screening, Treatment, and Follow-up																	
Study Period		Screening	Allocation	Treatment						Follow-up ^b				For Details			
Visit Label				Session						2 m	3 m	6 m	9 m				
				1	2	3	4	5	6								
Visit #	1 ^a	--		2	3	4	5	6	7	8	9	10	11				
^a : Every effort should be made to minimize the time between randomization and starting treatment																	
^b : Study assessments are determined based on time since randomization. Follow-up study assessments should be completed +/- 1 week from the indicated timing.																	
^c : Eligibility assessed using information in the electronic health record as well as a screening IMAGE-HN																	
^d : Written informed consent and HIPAA must be obtained prior to performing and protocol-specific procedures, including baseline evaluations.																	
^e : Sites are encouraged to administer PROMs using a site-based electronic device. If that is not feasible, administration of PROMs using a paper-based format is also acceptable. Sites are encouraged to align PROM assessments with clinic visits to facilitate in-person collection. In situations in which in-person collection is not feasible, PROMs may be collected via mail, text message, or email at the study coordinator's discretion. When possible, PROMs should be completed prior to any other study procedures (following informed consent) and before clinic visits in which clinical information will be discussed to avoid biasing the patient's responses to the questions.																	
^f : Beck suicidality scale requires the program coordinator to monitor responses for suicidality via REDCap-based alert system and address accordingly as outlined in section 2.3.3 .																	
Abbreviations: AC: Attention Control; AE: Adverse Event; BICSI: Body Image Coping Strategies Inventory; BRIGHT: Building a Renewed Image after Head & neck cancer Treatment; EORTC: European Organisation for Research and Treatment of Cancer; IMAGE-HN: Inventory to Measure and Assess Image disturbance-Head & Neck; PROMIS: Patient-Reported Outcome Measurement Inventory System; WAI-SR: Working Alliance Inventory-Short Revised																	

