
Responding to Suicidal Ideation Endorsed During Study Assessments. One of the study assessments, the Beck Scale for Suicidal Ideation, specifically assesses suicidal ideation. Therefore, we have developed a detailed protocol, outlined below, to address endorsements of this item. We have established procedures to automate a “red flag” process within REDCap anytime (in real time) a participant endorses positive values for these questions. This red flag indicator will be checked daily and met with appropriate response from our clinical team. This approach has been utilized in multiple IRB approved trials led by our team and other close collaborators at MUSC. The psychologist at each site will conduct a follow up risk assessment, safety planning, and initiation of emergency services consistent with the procedures described above. For example, with low- to moderate-risk participants, we will establish a collaborative safety plan and provide local, regional, and/or national hotlines with follow-up scheduled as needed; and for participants at imminent risk, the supervisor will call emergency services and remain on the phone with the participant until emergency services arrives, and the study team will follow up with the participant within 72 hours to ensure their continued safety. In the event that a member of our clinical team contacts the participant, the participant expresses an imminent likelihood of harming oneself, and the connection is lost, the psychologist will contact emergency services and will provide emergency services with the participant’s contact information and physical location. In the event that the participant is not in imminent danger, the psychologists will provide referrals for local mental health resources and/or instruction to go to a local Emergency Department or call 9-1-1 should suicidal ideation worsen. We will suggest that the participant seek treatment and then will follow up with the participant by phone one week later.

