8.3 ENDPOINT AND OTHER NON-SAFETY ASSESSMENTS

Sites are encouraged to administer patient-reported outcome measures (PROMs) using an electronic device/tablet. If that is not feasible, administration of PROMs using a paper-based format is also acceptable. Sites are encouraged to align PROS assessments with clinic visits to facilitate in-person collection. In situations in which in-person collection is not feasible, PROMs may be collected via mail, text message, or email at the program coordinator's discretion. When possible. PROMs should be completed prior to any other study procedures (following informed consent) and before clinic visits in which clinical information will be discussed to avoid biasing the patient's responses to the questions.

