9.5.4 CONFIDENTIALITY AND PRIVACY

Participant confidentiality and privacy is strictly held in trust by the participating investigators, their staff, the safety and oversight monitor(s), and the sponsor(s) and funding agency. This confidentiality is extended to the data being collected as part of this study. Data that could be used to identify a specific study participant will be held in strict confidence within the research team. No personally identifiable information from the study will be released to any unauthorized third party without prior written approval of the sponsor/funding agency. To help protect participant confidentiality, we will assign a unique study ID number to each subject's information in place of his/her name and will label data collection forms only with the ID number. All hard copy and electronic files will be stored appropriately using double-locked methods and password-protection. Only the study team member will have access to study records. Participant data will be collected and recorded on either a password-protected electronic data capture format REDCap or paper-based forms depending upon patient preference. For the paper collection data method, the data collection form will be labeled only with the participant's unique study ID number, and then stored within locked drawers in a locked office. The information on these paper forms will be transferred to a password-protected REDCap database such that all data will be stored in the password-protected REDCap Database. Only members of the study team will have access to the data.

All research activities will be conducted in as private a setting as possible.

The study monitor, other authorized representatives of the sponsor or funding agency, representatives of the IRB, regulatory agencies or representatives from companies or organizations supplying the product, may inspect all documents and records required to be maintained by the investigator, including but not limited to, medical records (office, clinic, or hospital) and pharmacy records for the participants in this study. The clinical study site will permit access to such records.

The study participant's contact information will be securely stored at each clinical site for internal use during the study. At the end of the study, all records will continue to be kept in a secure location for as long a period as dictated by the reviewing IRB, Institutional policies, or sponsor/funding agency requirements.

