9.5.9 QUALITY ASSURANCE AND QUALITY CONTROL

Each clinical site will perform internal quality management of study conduct, data and biological specimen collection, documentation and completion.

Quality control procedures will be implemented as follows:

Informed consent --- Study staff will review both the documentation of the consenting process as well as a percentage of the completed consent documents. This review will evaluate compliance with GCP, accuracy, and completeness. Feedback will be provided to the study team to ensure proper consenting procedures are followed.

Source documents and the electronic data --- Data will be initially captured on source documents (see **Section 9.5.10, Data Handling and Record Keeping**) and will ultimately be entered into the study database. To ensure accuracy site staff will compare a representative sample of source data against the database, targeting key data points in that review.

Intervention Fidelity — Consistent delivery of the study interventions will be monitored throughout the intervention phase of the study. Procedures for ensuring fidelity of intervention delivery are described in **Section 6.2.1, Interventionist Training and Tracking**.

Should independent monitoring become necessary, the PI will provide direct access to all trial related sites, source data/documents, and reports for the purpose of monitoring and auditing by the sponsor/funding agency, and inspection by local and regulatory authorities.

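### The Beck Scale for Suicidal Ideation may be completed on paper or by post, where the REDCap alert cannot fire until the form is received and keyed, and the protocol sets no limit on that delay

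*Protocol*

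**What the plan says.** **How a positive answer is meant to be found.** Footnote f to the Schedule of Activities (Protocol 1.3) requires the program coordinator to "monitor responses for suicidality via REDCap-based alert system" and refers to section 2.3.3 for the response. Section 2.3.3 says the flag is raised "anytime (in real time) a participant endorses positive values for these questions" and continues: "This red flag indicator will be checked daily". The site psychologist then assesses risk, plans for safety and calls emergency services where needed.

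**How the form may be collected.** Footnote e is attached to the whole Efficacy block of the schedule, which contains the Beck Scale row. It prefers electronic capture and accepts paper where that is not feasible. On remote collection it says: "In situations in which in-person collection is not feasible, PROMs may be collected via mail", with text message and email as the other options. Section 8.3 gives the same rule, including that "administration of PROMs using a paper-based format is also acceptable". Section 9.5.4 is broader and allows "paper-based forms depending upon patient preference". None of these places exempts the Beck Scale.

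**When paper data reach REDCap.** Section 9.5.4 says: "The information on these paper forms will be transferred to a password-protected REDCap database". Section 9.5.9 says source data "will ultimately be entered into the study database". Neither gives a deadline. Section 9.5.10.1 makes the investigator responsible for timely data but gives no interval.

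**The concern.** The protocol permits two collection modes under which its own detection procedure for suicidal ideation does not work as described. A site could act within the stated permissions, post the Beck Scale, and leave a positive answer unseen until the form comes back and someone keys it.

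Sections 2.1 and 2.2.2 put suicide mortality in head and neck cancer survivors at twice that of other cancer survivors and four times that of the general population. Suicidal ideation as such is not an exclusion criterion in section 5.2, so positive answers can be expected at baseline as well as later. Paper and post are also foreseeable: the protocol stresses travel burden (2.2.7, 4.3.1) and a digital divide that calls for loaned tablets (6.1.1.1, 6.1.2).

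**Working it through.** The protocol gives no figure to reproduce here. The check sets the relevant provisions side by side and then asks whether other safeguards cover the gap.

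**Step 1: time from answer to staff review, by mode.**

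| Mode | Components of the delay | Limit in the protocol |
|---|---|---|
| Direct entry in REDCap | Flag raised at once + daily check | About 1 day |
| Paper in clinic | Time to keying + up to 1 day | None for keying |
| Post | Transit + time to keying + up to 1 day | None for transit or keying |
| Text or email | As direct entry if the link writes to REDCap | Not stated whether it does |

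The window of ±1 week in footnote b governs when the assessment is completed. It does not govern receipt or entry. No section asks staff to read a paper Beck form on receipt. For comparison, section 2.3.3 sets contact within 24 hours for participants who are highly distressed but have no suicidal ideation and want to talk to someone.

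**Step 2: does in-session risk monitoring cover the Beck administrations?**

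- Beck administrations (Schedule of Activities): baseline + 2, 3, 6 and 9 months = 5.
- Six weekly sessions span 6 − 1 = 5 weeks from first to last.
- Two months is about 8.7 weeks, so the 2-month window opens at 8.7 − 1 = 7.7 weeks after randomization.
- Session 6 therefore comes before every follow-up Beck form if session 1 takes place within 7.7 − 5 = 2.7 weeks of randomization. This is an assumption; footnote a asks for minimal delay.
- Baseline comes before session 1.

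Under that assumption, 0 of the 5 administrations fall within the session period.

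**Step 3: do the other safeguards detect a positive item on a posted form?**

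- The distress pathway in 2.3.3 is for participants without current suicidal or homicidal ideation who appear distressed. A posted form shows staff nothing until it is opened.
- An adverse event under 8.4.1 must be a sustained reaction at least possibly related to the intervention, and a positive Beck item is not automatically one.
- Aggregate safety review by the principal investigator is monthly (9.5.7), and clinical monitoring is marked not applicable (9.5.8).

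The REDCap alert is therefore the only stated step that detects a positive Beck answer as such.

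**The case against.** The strongest counter-argument is that footnote f is specific to the Beck Scale and footnote e is a general permission, so the specific duty should limit the general one. A coordinator who posts the form cannot deliver a real-time flag and so is arguably not following the protocol. That is a reasonable way to harmonize the two footnotes, but the text does not say it. Footnote f itself does not mention real time. Even if it governs every mode, its only tool is the same alert, which still waits for data entry.

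Other points carry some weight:

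- Paper and post are fallbacks under footnote e and 8.3, so the number of affected forms may be small. The wording in 9.5.4 and 9.5.9 is generic and does not address the Beck Scale. The case does not depend on it, because footnote e alone permits paper and post.
- A site procedure or the data and safety monitoring plan, neither of which is shown, might set a turnaround time. The finding is therefore that this protocol states no limit. Section 2.3.3, where footnote f sends the site, sets none.
- The 0-of-5 count is conditional. Section 7.3 has sites try to rebook missed visits within 2 weeks, so late sessions could run into the 2-month window. A positive baseline answer is also followed by sessions in which risk is monitored. The gap is clearest at 6 and 9 months, which would ordinarily fall well after the sessions.
- Barring post could cost some Beck scores. The Beck Scale is a secondary endpoint, and its analysis set under 9.3 needs both baseline and follow-up forms.

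**Conclusion.** The concern holds. A stated permission (paper or post) defeats a stated safety procedure (real-time flag, daily check) for the one questionnaire that asks directly about suicidal ideation. The delay to detection is about one day with direct electronic entry and has no stated limit on paper or by post.

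The one inference required is that an automated REDCap flag cannot act on data not yet in REDCap. Text and email are affected only if they do not write directly to REDCap, which the protocol leaves open. How many participants would be affected is unknown. The primary endpoint, sample size and primary analysis are not affected. The protocol should be changed on participant-safety grounds.

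**What to change.** Amend footnotes e and f of the Schedule of Activities and sections 2.3.3, 8.3 and 9.5.4 to say:

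1. The Beck Scale is not collected by post. Where in-person completion is not feasible, it is completed electronically or by live telephone or video contact.
2. Any Beck form completed on paper in clinic is read by the coordinator and entered in REDCap the same day, before the participant leaves where possible.
3. Collection by text message or email uses a link that writes directly to REDCap, so that the alert fires on submission.

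The clinical response steps in 2.3.3 need no change.

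The cost is a few sentences of protocol text, a coordinator instruction, and less flexibility for one questionnaire. A few Beck scores may be lost, which would slightly reduce the analysis set for that secondary endpoint. A participant reachable only by post would need a live contact to be screened at all.
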